8.4 Pregnancy

Pregnancy occurring in the partner of a participant and up to 90 days after the completion of the study treatment should also be reported to the investigator and the NHMRC Clinical Trials Centre. The investigator should counsel the patient and their partner; discuss the risks of continuing with the pregnancy and the possible effects on the foetus.

The NHMRC Clinical Trials Centre must be notified within 24 hours and the participant's partner followed during the entire course of the pregnancy and postpartum period. After obtaining participant and partner consent, parental and neonatal outcomes will be recorded even if they are completely normal.

9 CENTRAL REVIEW

9.1 Screening for eligibility

^{68}Ga -PSMA PET/CT images will be reviewed centrally to confirm the eligibility of participants. Details for submitting images are in the Nuclear Medicine Manual. Confirmation of eligibility will be on a combination of both central and local reads.

PSMA 11 will be provided to each site to manufacture imaging of ^{68}Ga -PSMA-11.

9.2 Imaging

Reports and images of CT and bone scan imaging for tumour assessments will be submitted centrally. Details for submitting imaging reports are in the Study Manual.

10 NUCLEAR MEDICINE QUALITY ASSURANCE

Prior to beginning enrolment, all nuclear medicine imaging sites will be certified by the Australasian Radiopharmaceutical Trials Network (ARTnet). This will include certification of (1) ^{68}Ga -PSMA production, (2) ^{68}Ga -PSMA PET/CT phantom acquisition, (3) ^{177}Lu -PSMA-617 production and (4) ^{177}Lu SPECT/CT phantom acquisition. Methods for these in addition to recommended radiation protection precautions are detailed in the Nuclear Medicine Manual.

11 STORAGE OF BIOSPECIMENS

11.1 Central Blood Collection

Central laboratories will be used to conduct translational research studies including biomarker analyses. Translational research bloods will be collected, initially processed and stored at each site. Samples will later be shipped to a central facility for translational research and storage. Some blood may be collected and shipped in real-time to a central lab (such as Covance, Singapore and Epic Sciences, San Diego, USA) for circulating tumour cell (CTC) studies. Refer to the Biological Sampling Manual for procedures.

11.2 Central Tissue collection

Archival tissue will be retrieved for translational research from all participants. Additional fresh tissue biopsies (at baseline and at progression) may be collected for translational research from consenting participants. This is optional. Fresh tissue may be used for single-cell RNA studies. Samples will be

shipped to central laboratories for translational research and storage. Refer to the Biological Sampling Manual for procedures.

12 STUDY TREATMENT SUPPLY AND ACCOUNTABILITY

12.1 *Study Treatment*

The investigational agents are enzalutamide and ^{177}Lu PSMA-617.

PSMA-617 is a small molecule ligand that binds to the extra-cellular domain of the prostate-specific membrane antigen. Each vial is supplied with a chemical purity $\geq 95\%$. Lutetium-177 (^{177}Lu) is a nuclear reactor-produced radiometal with a half-life of 6.7 days. Its decay mode is beta Max 0.5 MeV, average beta 0.13 MeV and gamma 208 keV (11% abundance). It is supplied in the chemical form of Lutetium Chloride (LuCl_3) in 0.04 M HCl with a radionuclide and radiochemical purity of $>99\%$.

No carrier added (n.c.a.) ^{177}Lu and PSMA-617 will be provided as clinical trial stock. The final product ^{177}Lu -PSMA-617 will be compounded on site according to the Nuclear Medicine Manual by a qualified radiopharmacist or radiochemist. Quality control will be performed with HPLC prior to release of product. The study drug will be administered to eligible participants under the supervision of the nuclear medicine investigator or identified co-investigators.

12.2 *Control Treatment*

Enzalutamide is an androgen receptor inhibitor. It is provided as liquid-filled soft gelatine capsules each containing 40 mg enzalutamide for oral administration. Each carton contains 112 capsules. The inactive ingredients are caprylocaproyl polyoxylglycerides, butylated hydroxyanisole, butylated hydroxytoluene, gelatine, sorbitol sorbitan solution, glycerin, purified water, titanium dioxide, and black iron oxide.

Cartons of enzalutamide should be stored below 25°C (77°F) in a dry place.

Full details on product handling information are provided in the Product information, Investigator Brochure and Pharmacy Manual.

12.3 *Drug Accountability*

The radiopharmacy within the nuclear medicine department at participating institutions will maintain a record of ^{177}Lu and PSMA (both PSMA-11 and PSMA-617) supply and use. A record will be maintained of the Lu-PSMA prepared for each participant. The radiopharmacy will also maintain a record of receipt and product destruction as appropriate. The oncology pharmacy will maintain a record of enzalutamide dispensed for each participant and subsequent returns. Enzalutamide compliance will be assessed at Day 15 and Day 43 (± 7 days). The oncology pharmacy will also maintain a record of drug receipt and drug destruction as appropriate. Participants will be asked to return unused drug and empty drug containers at each return visit. Drug accountability logs will be requested, as required, from each pharmacy for central review by each regional coordinating centre.

12.4 *Background treatment*

Androgen deprivation therapy will be provided according to usual practice. Drug accountability will not be performed for androgen deprivation therapy.

13 STATISTICAL CONSIDERATIONS

13.1 Sample Size

The study will randomise patients to the experimental combination of enzalutamide and Lu-PSMA versus enzalutamide alone in a 1:1 ratio. A sample size of 160 patients recruited over 12 months and followed until 150 events occurred (approximately another 18 months), provides 80% power at the two-sided 5% level of significance to detect a HR of 0.625 assuming a median PSA PFS of 5 months in the enzalutamide alone arm whilst allowing for non-adherence to assigned treatment in up to 2 participants.

13.2 Statistical Analysis

A statistical analysis plan will be finalised prior to data-lock, and contain additional detail on the methods described below.

All randomised participants will be eligible for inclusion in the full analysis set in accordance with the intention-to-treat analysis principle. Analysis of efficacy endpoints will be undertaken on participants in the full analysis set. A sensitivity analysis using a per-protocol analysis set may be performed on efficacy endpoints. The safety population will comprise all randomised participants who received at least one administration of study medication. Participants will be analysed according to the regimen they actually received for the purposes of the safety analysis.

All p-values and confidence intervals will be two-sided.

The primary analysis will be a comparison of PSA PFS in the two treatment arms using a log-rank test accounting for clinical stratification factors. Kaplan-Meier curves for PSA PFS will also be prepared. An estimate of the hazard ratio will be obtained using Cox proportional hazard regression accounting for clinical stratification factors. Other time-to-event endpoints will be analysed in a comparable fashion to the primary endpoint.

Treatment groups will be compared on binary endpoints (e.g. PSA response) using a Cochran–Mantel–Haenszel χ^2 test accounting for the clinical stratification factors. Multivariable logistic regression will be used to estimate odds ratios with confidence intervals for covariates and assigned treatment.

Scale scores from the QLQ-C30 and PDF will be summarised by group over time. The applicability of repeated measures mixed modelling to these scales will be investigated. This will involve fitting a linear mixed model with patient as the random effect, and fixed effect terms for treatment allocation, time point, a time point-by-treatment allocation interaction, and the baseline assessment.

The analysis of safety data will be principally descriptive in nature. Adverse Events (AEs) and Serious Adverse Events (SAEs) will be tabulated by treatment allocation and CTCAE v5.0 criteria including system organ class, term, and worst grade.

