1.2 Androgen Receptor Signalling Inhibition

Enzalutamide is a targeted androgen-receptor inhibitor that competitively binds to the ligand-binding domain of the androgen receptor and inhibits androgen-receptor translocation to the cell nucleus, recruitment of androgen-receptor cofactors, and androgen-receptor binding to DNA. Enzalutamide improved survival in men with mCRPC that had progressed after chemotherapy (22). Subsequently, in a double-blind, phase 3 study (PREVAIL) comparing enzalutamide with placebo in the pre-chemotherapy setting, enzalutamide significantly decreased risk of radiographic progression and death while delaying initiation of chemotherapy in men with mCRPC (23). However, there is a significant proportion of men who fail to derive prolonged benefit from androgen signalling inhibition with enzalutamide, with 50% of men demonstrating PSA progression by 11 months (23).

Risk factors that help to predict poor responses to enzalutamide include the presence of AR-V7 splice variants, anaemia, radiographic progression prior to commencing treatment, elevated LDH or ALP, rapid PSA velocity, liver metastases and short time since diagnosis. In men with these risk factors, median time to PSA progression can be as short as 5.6 months (IQR 3.4-8.3) compared to 14.5 months (IQR 11.3-19.1) for men without these risk factors (24). The PROPHECY trial presented at the 2018 ASCO ASM evaluated the ability of AR-V7 splice variants to predict treatment response to enzalutamide in men with mCRPC who had 2 or more high risk features. The presence of AR-V7, as detected using the EPIC CTC AR-V7 assay, independently predicted both a shorter overall survival (OS) and a shorter radiographic progression free survival (rPFS) in men receiving enzalutamide. Though this biomarker appears to predict for a shorter duration of benefit, lack of a

proven alternative strategy renders this knowledge prognostic at best and therefore does not improve treatment outcomes. However, if AR-V7 was found to have a strong correlation to PSMA expression and upregulation, combination therapy using androgen signalling inhibition and PSMA targeted therapy could well improve treatment response in those men who are AR-V7positive and predicted to have a poor response to enzalutamide alone.

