3 DESIGN

Randomised, phase 2, stratified, multicentre, open label clinical trial.

Participants will be randomised to enzalutamide or enzalutamide and Lu-PSMA in a 1:1 ratio. A minimisation approach will be used to minimise chance imbalances across the following stratification factors: study site, volume of disease (>20 versus ≤ 20 sites of disease measured on ^{68}Ga -PSMA PET/CT), prior treatment with early docetaxel for castration-sensitive disease (yes vs no), and prior treatment with abiraterone (yes vs no).

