4.2 Inclusion Criteria

1. Males aged 18 or older with metastatic adenocarcinoma of the prostate defined by:
 - Documented histopathology of prostate adenocarcinoma (no features of neuroendocrine carcinoma)
 - OR
 - Metastatic disease typical of prostate cancer
2. Castration-resistant prostate cancer (defined as disease progressing despite castration by orchectomy or ongoing luteinising hormone-releasing hormone agonist or antagonist).
3. Progressive disease with rising PSA defined by PCWG3 criteria (sequence of 2 rising values at a minimum of 1-week intervals) AND $\text{PSA} \geq 5 \text{ ng/mL}$.
4. At least 2 of the following risk factors for early treatment failure with enzalutamide:
 - i. $\text{LDH} \geq \text{ULN}$
 - ii. $\text{ALP} \geq \text{ULN}$
 - iii. $\text{Albumin} < 35 \text{ g/L}$
 - iv. De novo metastatic disease (M1) at initial diagnosis *
 - v. < 3 years since initial diagnosis
 - vi. > 5 bone metastases *
 - vii. Visceral metastases *
 - viii. PSA doubling time < 84 days
 - ix. Pain requiring opiates for > 14 days
 - x. Prior treatment with abiraterone
- * Based on conventional imaging (CT and/or bone scan)
5. Target or non-target lesions according to RECIST 1.1 (Appendix 1) or PCWG3 (Appendix 3)
6. Significant PSMA avidity on ^{68}Ga -PSMA PET/CT, defined as $\text{SUV}_{\text{max}} > 15$ at a single site (regardless of lesion size) and $\text{SUV}_{\text{max}} > 10$ at sites of disease $\geq 10\text{mm}$ (unless subject to factors explaining a lower uptake, e.g. respiratory motion, reconstruction artefact)
7. ECOG performance status 0-2 (Appendix 2)
8. Adequate renal function:
 - Creatinine clearance $\geq 40\text{mL/ min}$

9. Adequate liver function:
 - Bilirubin < 1.5 x upper limit of normal (ULN) (or if bilirubin is between 1.5 - 2x ULN, must have a normal conjugated bilirubin)
 - AST or ALT ≤ 2.0 x ULN (or ≤ 5.0 x ULN in the presence of liver metastases)
10. Adequate bone marrow function:
 - Platelets ≥ 100 x10⁹/L
 - Haemoglobin ≥ 90g/L (no red blood cell transfusion in last 4 weeks)
 - Neutrophils > 1.5 x10⁹/L
11. Estimated life expectancy > 12 weeks
12. Study treatment both planned and able to start within 21 days of randomisation
13. Willing and able to comply with all study requirements (including both treatments: enzalutamide and Lu-PSMA), and all required study assessments
14. Signed, written, informed consent

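### The primary PSA-PFS analysis adjusts only for the clinical stratification factors and omits prognostic baseline values measured on every man: a missed efficiency, not an error

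*Protocol*

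**What the plan says.** On the primary test, section 13.2 says: "The primary analysis will be a comparison of PSA PFS in the two treatment arms using a log-rank test accounting for clinical stratification factors". The effect estimate carries the same restriction: "An estimate of the hazard ratio will be obtained using Cox proportional hazard regression accounting for clinical stratification factors". Section 13.2 does not list the factors. Section 3 names four for minimisation: study site, disease volume (more than 20 sites against 20 or fewer), early docetaxel and prior abiraterone. I read the word clinical as excluding site, which leaves three.

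Section 13.1 plans 160 men and 150 events and takes 5 months as the control-arm median. It says the design "provides 80% power at the two-sided 5% level of significance to detect a HR of 0.625".

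Three other places bear on the choice:

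- Section 1.2 lists predictors of poor response to enzalutamide, among them LDH, ALP, PSA velocity, liver metastases and short time since diagnosis. It says of men with such factors that "median time to PSA progression can be as short as 5.6 months (IQR 3.4-8.3) compared to 14.5 months" for men without them.
- Section 4.2, criterion 4, makes a related list a condition of entry: "At least 2 of the following risk factors for early treatment failure with enzalutamide". Ten features follow, the tenth being prior abiraterone.
- Section 6.1 schedules PSA and blood tests at screening for all participants. Its note 3 lists ALP and LDH among those tests; albumin is not listed.

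**The concern.** The protocol regards these features as prognostic enough to select patients on, and measures several of them in everyone. Apart from prior abiraterone, and partial overlap between disease volume and the bone-metastasis feature, none enters the primary model. Nor does the baseline value of PSA, the marker that defines the endpoint.

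In a log-rank or Cox analysis, leaving out a strong prognostic variable pulls the hazard ratio towards 1 and costs power, even when the arms are balanced on it. Power has little slack here, so a few points recovered from data already collected would be worth having.

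**Working it through.** **1. The plan's own figure.** Inputs from section 13.1: HR 0.625, two-sided 5%, 80% power, 1:1 allocation, 150 events.

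- Freedman: events = (1.96 + 0.842)² × [(1 + 0.625)/(1 − 0.625)]² = 7.85 × 18.78 = 147.4, so 148. Power at 150 events: √150 × 0.375/1.625 − 1.96 = 0.866, giving 80.7%.
- Schoenfeld: events = 4 × 7.85/(ln 0.625)² = 31.4/0.2209 = 142.1, so 143. Power at 150 events: (√150/2) × 0.470 − 1.96 = 0.918, giving 82.1%. Diluting for 2 non-adherent men of 80 in one arm: 143/(1 − 0.025)² = 150.4.

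Both routes reach about 150 with no covariates. The stated power is right.

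**2. An anchor for prognostic strength.** The only figure is in section 1.2: 14.5/5.6 = 2.59, a hazard ratio of about 2.6 if times are exponential. For a 50:50 split, the SD on the log-hazard scale is ln 2.59 × 0.5 = 0.951 × 0.5 = 0.48. This contrasts men with and men without risk factors. Every man in this trial has at least two, so the spread inside the trial is probably smaller and 0.48 is an upper anchor.

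**3. Simulated gain.** Settings from the plan: 160 men, 12 months of accrual, analysis at the 150th event, control median 5 months. Assumptions: exponential times, HR 0.625 at a given prognosis, three binary stratification factors with log-HRs 0.4, 0.2 and 0.4, and two further covariates whose combined log-hazard SD is varied. There were 1,500 trials per setting, so each power has a Monte Carlo error of about 1 point.

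| Covariate SD | Stratified log-rank | Cox, three factors | Cox, three factors + two covariates |
|---|---|---|---|
| 0 | 77% | 81% | 81% |
| 0.2 | 74% | 78% | 81% |
| 0.3 | 74% | 78% | 82% |
| 0.4 | 71% | 74% | 81% |
| 0.5 | 67% | 71% | 81% |

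The last two columns isolate the covariates: gains of 0, 3, 4, 7 and 10 points. Two further simulations of this comparison gave 0 points at SD 0 and 3 to 4 at SD 0.3. At the top of the range, one gave 9 to 10 over SD 0.4 to 0.5 and the other 13 at SD 0.5. The step from the log-rank column to the first Cox column (3 to 4 points) comes from entering the factors as covariates instead of strata, and should not be credited to the new covariates.

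**4. Check by formula.** With a conditional HR of 0.625, the HR averaged over simulations in the analysis without covariates was 0.644 at SD 0.3 and 0.667 at SD 0.5. Schoenfeld power at 150 events is then:

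- SD 0.3: 6.124 × 0.4405 − 1.96 = 0.738, giving 77%.
- SD 0.5: 6.124 × 0.4047 − 1.96 = 0.518, giving 70%.

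Against 82% at 0.625 these are losses of about 5 and 12 points, in line with the simulation.

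**5. Which scale 0.625 is on.** The above takes 0.625 as the HR at a given prognosis. If the HR seen by the planned analysis is instead about 0.61, the stratified log-rank test keeps 80% to 81% power. Adding five covariates to a stratified Cox model then takes it to 84% at SD 0.3 and 89% at SD 0.5. On that reading, adjustment is a bonus on top of an intact 80%.

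**6. Type I error.** Under HR = 1 with five covariates, the stratified log-rank test rejected in 5.5% of trials and the adjusted Wald tests in 6.1% to 6.8% (Monte Carlo error 0.6 points). Part of any apparent gain, perhaps a point, is therefore mild anti-conservatism of the Wald test.

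**The case against.** The case for leaving section 13.2 alone is fair. A log-rank test and Cox model accounting for the allocation factors is a conventional analysis that matches the randomisation. Nothing is contradicted and the stated power reproduces. The SAP, which is not at hand, may add adjusted supporting models. The gain rests on a prognostic strength that the protocol does not supply, and the range includes zero. All of this stands. It makes the point an improvement on a stated choice, but does not remove it: section 13.2 already fixes the primary test and leaves only further detail on it to the SAP.

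Several stronger readings might be inferred, and the protocol does not support them:

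- *The trial is underpowered.* It is not, on its own assumptions.
- *The 2.6 ratio applies here.* It compares men with and without risk factors, and the lists in sections 1.2 and 4.2 overlap only in part.
- *All the risk features are ignored.* Prior abiraterone is adjusted for, and disease volume partly covers bone metastases.
- *All ten features are available on every man.* Entry needs two, nothing says the rest are recorded, and albumin is not among the scheduled tests.
- *Baseline PSA level is shown to be prognostic.* Section 1.2 names PSA velocity; using the level is a statistical judgement.
- *Chance imbalance in the risk features would bias the result.* Randomisation and the test's error rate already allow for it.

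**Conclusion.** The point holds as a missed efficiency. Section 13.2 restricts the primary analysis to three clinical factors and passes over baseline values that every man provides, some of which the protocol itself ties to early PSA progression.

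Measured against a Cox model with the three factors, the covariates would add about 0 points of power if uninformative, 3 to 4 at a log-hazard SD of 0.3, and 10 or more at 0.5. The top of that range lies close to the 0.48 anchor and is unlikely to be exceeded in a population selected for high risk. These sizes rest on exponential times, the assumed effects of the stratification factors, and 0.625 being the HR at a given prognosis. With uninformative covariates, adding two cost nothing measurable, so the balance favours adjustment even though the gain is uncertain.

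**What to change.** In section 13.2, and in the SAP before data lock, pre-specify the primary test as the treatment term of a Cox model containing:

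- the three clinical stratification factors;
- log baseline PSA, LDH and ALP;
- time since initial diagnosis, if it is recorded for all men.

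Test treatment by likelihood ratio instead of Wald, in view of the rejection rates in step 6, and report the stratified log-rank test beside it. State how an occasional missing covariate value is handled. Because the trial is open label, settle the list without sight of outcomes by arm. Do not use a count of all ten features unless each one is confirmed as recorded for every man.

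The cost is a short change to section 13.2, with no new patients, visits or scheduled tests. There are two small downsides. The hazard ratio becomes conditional on the covariates, so section 13.1 should say whether 0.625 is meant on that scale or on the scale of the stratified comparison. A few more parameters are also fitted, which about 150 events can carry.

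### The mixed model described for QLQ-C30 and PDF scores omits the clinical stratification factors that the log-rank, Cox and CMH analyses use: a small, conditional loss of precision

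*Protocol*

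**What the plan says.** On allocation, Protocol section 3 states: "A minimisation approach will be used to minimise chance imbalances across the following stratification factors". The factors are study site, volume of disease (>20 vs ≤20 sites on PSMA PET/CT), early docetaxel (yes/no) and prior abiraterone (yes/no).

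Section 13.2 then sets out the analyses:

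- **Primary endpoint:** a "log-rank test accounting for clinical stratification factors", with the hazard ratio from "Cox proportional hazard regression accounting for clinical stratification factors".
- **Other time-to-event endpoints:** "Other time-to-event endpoints will be analysed in a comparable fashion to the primary endpoint".
- **Binary endpoints:** a CMH test that accounts for the clinical stratification factors. The odds ratios come from a logistic regression whose covariates are not named.
- **QLQ-C30 and PDF scores:** summaries by group over time. In addition, "The applicability of repeated measures mixed modelling to these scales will be investigated". The model in view has a random term for each man, and its remaining terms are given as: "fixed effect terms for treatment allocation, time point, a time point-by-treatment allocation interaction, and the baseline assessment".

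The section opens by leaving further detail to another document: "A statistical analysis plan will be finalised prior to data-lock, and contain additional detail on the methods described below".

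**The concern.** Minimisation makes the arms alike on the chosen factors, which reduces the true sampling variation of the treatment difference if those factors predict the outcome. A model that leaves them out does not recognise this. The variance they explain stays in the error term, so the reported standard error is larger than the true one. The log-rank, Cox and CMH analyses avoid the problem by carrying the factors. The listed terms of the mixed model do not.

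Health-related quality of life (HRQL) is a stated trial objective, and the protocol gives no effect size or power for it. If the factors matter for these scores, confidence intervals would be wider than the design warrants. A real difference in either direction would then be a little more likely to go undetected.

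**Working it through.** **The plan's own figures.** The protocol states no variance, effect size or power for the HRQL scores, so there is no HRQL figure to reproduce. The stated sample size concerns PSA PFS only (section 13.1: 150 events, 80% power, HR 0.625, two-sided 5%, 1:1), and it reproduces:

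- Schoenfeld: 4(1.96 + 0.84)²/(ln 0.625)² gives 143 events.
- Freedman: (1.96 + 0.84)² × (1.625/0.375)² gives 148 events.
- With 150 events, and the log hazard ratio diluted by 2/80 for two non-adherent men, power is 80.1%.

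The present point does not touch this calculation.

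**Inputs for the HRQL model.** From the documents: 160 men, 1:1 allocation, minimisation on the four factors, and the listed fixed effects. Assumed: R², the share of variance in a man's mean follow-up score that the three clinical factors explain after the baseline score. Because it is unknown, a range starting at zero is used.

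**Formulas.** With the factors balanced between arms:

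- Reported SE without the factors, divided by SE with them = 1/√(1 − R²).
- True size of a nominal 5% test without the factors = 2[1 − Φ(1.96/√(1 − R²))].
- Power without the factors, where the adjusted model has 80% = Φ(2.80 − 1.96/√(1 − R²)).

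For R² = 0.10, the SE ratio is 1/√0.90 = 1.054. The effective critical value is 1.96 × 1.054 = 2.066, so the true size is 3.9% and power is Φ(0.74) = 76.9%.

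| Assumed R² | SE ratio | True size | Power without factors, formula (80% with) | Simulated power, without v with |
|---|---|---|---|---|
| 0 | 1.00 | 5.0% | 80.0% | 80.1% v 80.2% |
| 0.02 | 1.01 | 4.8% | 79.4% | 79.2% v 79.4% |
| 0.05 | 1.03 | 4.4% | 78.5% | 77.4% v 79.1% |
| 0.10 | 1.05 | 3.9% | 76.9% | 75.3% v 79.0% |
| 0.20 | 1.12 | 2.8% | 72.9% | 72.2% v 79.1% |

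**Simulation.** The last column uses 160 men, 12 sites, biased-coin minimisation with probability 0.8, and factor prevalences of 50%, 50% and 20%. There were 1,500 runs per setting, with an effect sized to give about 80% power after adjustment. All these settings are assumptions. The analysis is a linear model on each man's mean score, which stands in for the random-intercept model when data are complete.

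At R² = 0.10 the unadjusted model reported an SE of 0.158, while the estimates actually varied with an SD of 0.150 to 0.153. Under no effect, the unadjusted test rejected in 2.5% to 4.6% of runs across settings and never exceeded 5%. Monte Carlo error is about 0.6 points for these rates, √(0.05 × 0.95/1500), and about 1 point for power.

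A second simulation with 10 sites and a coin of 0.85, at an effect of 0.4 residual SD, gave 70.1% v 71.7% power at R² = 0.05 and 73.0% v 76.4% at 0.10. Its null rejection rates without the factors were 4.7% and 4.0%. The two simulations agree on direction and rough size.

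**The case against.** Several points on the other side stand.

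- **The model is provisional.** A reader might infer that the HRQL model is fixed without the factors. The text does not support that: the protocol will only investigate whether mixed modelling applies, and the SAP is to add detail. Nothing bars further terms. Even so, the protocol is not silent here. It writes out the terms, and an SAP that follows the list literally would carry the omission forward.
- **The contrast is not with every other analysis.** A reader might infer that the HRQL model alone lacks the factors. The logistic regression for binary endpoints does not name them either. The contrast holds for the time-to-event analyses and the CMH test.
- **The loss is conditional.** A reader might infer that the standard errors are certainly too large. The model already adjusts for the baseline score, and no figure in the protocol shows that the three factors add to it. At R² = 0 nothing is lost, and at 0.02 almost nothing.
- **The calculation simplifies.** Under section 6.2.5 forms stop at radiographic progression, so men contribute unequal numbers of assessments. A contrast at a single visit also carries within-patient noise, which makes the factors' share of variance smaller than for a mean score. The power figures are illustrative.
- **Different adjustment by endpoint type is legitimate.** Adjusting for the baseline score in this model is sound. Adverse events are also graded and tabulated separately, so detection of harm does not rest on HRQL alone.

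**Conclusion.** The point holds as a minor one. The listed fixed effects omit the clinical factors on which men are minimised, while the log-rank, Cox and CMH analyses in the same section account for them. The consequence runs in one direction only: standard errors somewhat too large and a mildly conservative test, if and only if the factors predict HRQL beyond the baseline score. For an assumed partial R² between 0 and 0.10, the overstatement is 0% to about 5% and the power loss is nil to about 3 to 4 points. A larger R² would cost more, but nothing in the documents points to one.

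A reader might also infer that the HRQL comparison is biased or its error rate inflated. Neither follows: the treatment estimate is unbiased and the type I error is at or below nominal. The primary endpoint and its sample size are unaffected.

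**What to change.** In section 13.2, add volume of disease (>20 vs ≤20 sites), early docetaxel (yes/no) and prior abiraterone (yes/no) to the fixed effects of the QLQ-C30/PDF mixed model, or confirm them in the SAP. Site need not be added for consistency, because the other analyses refer only to the clinical factors.

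The cost is one line of wording and three degrees of freedom out of 160 men. The data are already recorded at randomisation. If the factors turn out to explain nothing, the simulated power is unchanged within error (80.1% without v 80.2% with). This is a low-priority improvement.
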